### 2.1. Modifications to the Analysis Plan Described in the Protocol

The dose escalation schema in section 1.2.1 of the Sub-Study A Protocol Amendment 8 does not capture all possible movement allowed by BLRM in combination studies. This SAP clarifies that opening lateral dose levels is possible, such as going from 3A to 4B, as is escalating from 4B to 4A, as long as the dose level to be opened satisfies the EWOC principle.

### 2.2. Study Objectives, Endpoints, and Estimands

#### Phase 1b

Type	Objectives	Endpoints	Estimands
Primary			
Safety	
 
To assess safety and tolerability of elranatamab in combination with nirogacestat in participants with RRMM in order to select a RP2D(s) for the combination
 
	
 
DLTs during DLT observation period.
 
	
 
The primary estimand is DLT rate estimate based on data from DLT-evaluable participants during the DLT observation period, which is approximately 35 days from COD1 through the end of C1.
 

Secondary			
Safety	
 
To evaluate the overall safety profile
 
	
 
AEs as characterized by type, frequency, severity (as graded by NCI CTCAE version 5.0), timing, seriousness, and relationship to elranatamab in combination with nirogacestat. The severity of CRS and
 
	
 
N/A
 

090177e1a0f4f44c\Approved\Approved On: 14-Jun-2024 22:12 (GMT)

		
ICANS will be assessed according to ASTCT criteria (Lee et al, 2019).
 
 
Laboratory abnormalities as characterized by type, frequency, severity (as graded by NCI CTCAE v5.0), and timing.
 
	
Efficacy	
 
To evaluate anti-myeloma activity of elranatamab in combination with nirogacestat.
 
	
 
ORR and CRR, per IMWG response criteria as determined by investigator;
 
Time to event endpoints: TTR, DOR, DOCR and PFS per IMWG response criteria as determined by investigator, and OS;
 
MRD (assessed by central lab) negativity rate per IMWG sequencing criteria.
 
	
 
N/A
 

PK	
 
To evaluate the PK of elranatamab given alone and in combination with nirogacestat. Additionally, PK of nirogacestat will be evaluated when administered with elranatamab
 
	
 
Pre- and post-dose concentrations of elranatamab;
 
Trough serum concentrations of nirogacestat at selected cycles.
 
	
 
N/A
 

Immunogenicity	
 
To evaluate immunogenicity of elranatamab in combination with nirogacestat.
 
	
 
Incidence and titers of ADA and NAb against elranatamab.
 
	
 
N/A
 

Exploratory			
Biomarker	
 
To explore the relationship between elranatamab and nirogacestat and the biology of the participant's MM.
 
	
 
Measurements of biomarkers (DNA, RNA, protein or defined cell types) resulting from analyses of peripheral blood and/or BM biospecimens.
 
	
 
N/A
 

	
 
To explore correlations between elranatamab exposure and efficacy, safety, and biomarker endpoints, if data allow.
 
	
 
Selected PK, efficacy, safety, and biomarker endpoints.
 
	
 
N/A
 

090177e1a0f4f44c\Approved\Approved On: 14-Jun-2024 22:12 (GMT)

**Phase 2**

Type	Objectives	Endpoints	Estimands
Primary			
Efficacy	
 
To assess the clinical efficacy of elranatamab in combination with nirogacestat.
 
	
 
ORR per IMWG response criteria as determined by investigator.
 
	
 
The primary estimand is the treatment effect of elranatamab in combination with nirogacestat on ORR per IMWG response criteria as determined by investigator. It will be estimated based on all enrolled RRMM participants who received at least 1 dose of study intervention. All data collected after an intercurrent event of subsequent anticancer therapy will be excluded. All response assessments regardless of gaps in disease assessments will be considered. The median and its corresponding 2-sided 90% credible interval of ORR based on the posterior distribution will be calculated.
 

Secondary			
Efficacy	
 
To determine additional efficacy outcomes of elranatamab in combination with nirogacestat.
 
	
 
CRR per IMWG criteria as determined by investigator.
 
Time to event endpoints: TTR, DOR, DOCR and PFS per IMWG response criteria as determined by investigator, and OS.
 
MRD (assessed by central lab) negativity rate per IMWG sequencing criteria.
 
	
 
N/A
 

Safety	
 
To further characterize the overall safety profile and tolerability of elranatamab in combination with nirogacestat.
 
	
 
AEs as characterized by type, frequency, severity as graded by NCI CTCAE, version 5.0, timing, seriousness, and relationship to elranatamab in combination with other anti-cancer therapies. The severity of CRS and ICANS
 
	
 
N/A
 

090177e1a0f4f44c\Approved\Approved On: 14-Jun-2024 22:12 (GMT)

		
will be assessed according to ASTCT criteria (Lee et al, 2019).
 
 
Laboratory abnormalities as characterized by type, frequency, severity (as graded by NCI CTCAE v5.0), and timing.
 
	
PK	
 
To evaluate PK of elranatamab at the RP2D in combination with nirogacestat. Additionally, to collect PK data of nirogacestat when administered with elranatamab.
 
	
 
Trough concentrations of elranatamab and nirogacestat in selected cycles.
 
	
 
N/A
 

Immunogenicity	
 
To evaluate immunogenicity of elranatamab in combination with nirogacestat.
 
	
 
Incidence and titers of ADA and NAb against elranatamab.
 
	
 
N/A
 

Exploratory			
Biomarker	
 
To explore the relationship between elranatamab and nirogacestat and the biology of the participant’s MM.
 
	
 
Measurements of biomarkers (DNA, RNA, protein or defined cell types) resulting from analyses of peripheral blood, and/or BM biospecimens.
 
	
 
N/A
 

	
 
To explore correlations between elranatamab exposure and efficacy, safety and biomarker endpoints, if data allow.
 
	
 
Selected PK, efficacy, safety and biomarker endpoints.
 
	
 
N/A
 

### 2.3. Study Design

Sub-study A of C1071004 protocol will evaluate safety, efficacy, PK, and pharmacodynamics of elranatamab in combination with nirogacestat in in participants with RRMM.

The combination will be assessed in 2 parts in the sub-study:

- Phase 1b** part to evaluate the safety, tolerability, and select a recommended dose and regimen for the combination (combination RP2D).
- Phase 2** part to further evaluate the efficacy and safety of the combination.

090177e1a0f4f44c\Approved\Approved On: 14-Jun-2024 22:12 (GMT)

[figure not shown]
**Phase 1b Design:**

The number of participants to be enrolled in Phase 1b will depend on the number of dose levels evaluated and the number of participants treated at each dose level. Phase 1b dosing (dose level to be evaluated in the next cohort) and enrollment (number of participants to be enrolled in the next cohort) decisions will use an escalation model (BLRM approach) to determine the MTD of elranatamab when administered in combination with nirogacestat.

**Phase 2 Design:**

Phase 2 will begin once the combination RP2D from the Phase 1b is selected. Approximately 50 participants will be enrolled in the Phase 2 part to assess anti-tumor activity and safety of elranatamab in combination with nirogacestat.

**Figure 1. Study Design**

**3. ENDPOINTS AND BASELINE VARIABLES: DEFINITIONS AND CONVENTIONS**

**3.1. Primary Endpoints**

**Phase 1b**

The primary endpoint of the Phase 1b part is the incidence of DLTs in the DLT-Evaluable Set during the DLT observation period, which is approximately 35 days from C0D1 through the end of C1.

**Phase 2**

The primary endpoint in the Phase 2 part is ORR per IMWG response criteria, defined as the proportion of participants with an objective response per IMWG response criteria as determined by investigator.

Objective response is defined as having a best overall response (BOR) of confirmed stringent complete response (sCR), complete response (CR), very good partial response (VGPR) or partial response (PR).

For all efficacy endpoints per IMWG response criteria, BOR will be assessed based on reported overall responses recorded at evaluation time points from the date of first dose until

090177e1a0f4f44c\Approved\Approved On: 14-Jun-2024 22:12 (GMT)

the first documentation of confirmed PD, death or start of new anti-cancer therapy, whichever occurs first.

## **3.2. Secondary Endpoints**

### **3.2.1. Efficacy Endpoints**

For all efficacy endpoints per IMWG response criteria, BOR is assessed based on reported overall responses (per IMWG response criteria (Rajkumar et al, 2014)) recorded at evaluation time points from the date of first dose until the first documentation of confirmed PD, death or start of new anti-cancer therapy, whichever occurs first.

Objective response is defined as having a BOR of confirmed sCR, CR, VGPR, or PR.

#### **3.2.1.1. Complete Response Rate**

Complete response rate (CRR) is defined as the proportion of participants with a confirmed sCR or CR per IMWG criteria as determined by investigator.

#### **3.2.1.2. Duration of Response**

Duration of response (DOR) is defined, for participants with an objective response per IMWG criteria as determined by investigator, as the time from the first documentation of objective response that is subsequently confirmed, until confirmed PD per IMWG criteria, or death due to any cause, whichever occurs first.

#### **3.2.1.3. Duration of Complete Response**

Duration of complete response (DOCR) is defined, for participants with a BOR of confirmed sCR or CR per IMWG criteria as determined by investigator, as the time from the first documentation of sCR or CR that is subsequently confirmed, until confirmed PD per IMWG criteria, or death due to any cause, whichever occurs first.

#### **3.2.1.4. Progression-free Survival**

Progression-free survival (PFS) is defined as the time from the date of first dose until the confirmed PD per IMWG criteria as determined by investigator, or death due to any cause, whichever occurs first.

#### **3.2.1.5. Overall Survival**

Overall survival (OS) is defined as the time from the date of first dose until death due to any cause.

#### **3.2.1.6. Time to Response**

Time to response (TTR) is defined, for participants with an objective response per IMWG criteria as determined by investigator, as the time from the date of first dose to the first documentation of objective response that is subsequently confirmed.

#### **3.2.1.7. Minimal Residual Disease Negativity Rate**

Minimal Residual Disease (MRD) (assessed by central lab) negativity rate is the proportion of participants with CR or better with negative MRD per IMWG sequencing criteria from the

date of first dose until confirmed PD, death or start of new anticancer first therapy, whichever occurs first.

### 3.2.2. Safety Endpoints

- Adverse events (AEs) and laboratory abnormalities as graded by the National Cancer Institute Common Terminology Criteria for Adverse Events (NCI CTCAE) version 5.0.
- Cytokine release syndrome (CRS) and immune cell-associated neurotoxicity syndrome (ICANS) graded according to ASTCT criteria .

### 3.2.3. Pharmacokinetic Endpoints

#### Phase 1b

- PK parameters of elranatamab:  $C_{max}$ ,  $T_{max}$ ,  $AUC_{last}$  after elranatamab administration alone as a priming dose;
- Pre- and post-dose concentrations (free and total) of elranatamab in combination with nirogacestat;
- Trough serum concentrations of nirogacestat at selected cycles.

#### Phase 2

- Trough concentrations of elranatamab and nirogacestat in selected cycles.

### 3.2.4. Immunogenicity Endpoints

- Incidence and titers of ADA and NAb against elranatamab.

## 3.3. Exploratory Endpoints

### 3.3.1. Translational Oncology Biomarkers Endpoints

- Measurements of biomarkers (DNA, RNA, protein or defined cell types) resulting from analyses of peripheral blood, saliva and/or BM biospecimens.
- Selected PK, efficacy, safety, and biomarker endpoints

### 3.3.2. Patient-Reported Outcomes (Phase 2 Only) Endpoints

Patient-reported outcomes (PROs) are measured using the following instruments:

- European Organization for Research and Treatment of Cancer Quality of Life of Cancer Patients core module (EORTC QLQ-C30): EORTC QLQ-C30 is a well-known, reliable and valid self-administered questionnaire used in oncology trials. The QLQ-C30 contains 30 items and is grouped into five functional scales (physical, role, emotional, cognitive and social functioning), three symptom scales (fatigue, nausea/vomiting, and pain), six single items (dyspnea, insomnia, appetite loss, constipation, diarrhea and financial impact) and a global health status/quality of

life (QoL) scale. The questionnaire uses 4-point Likert scales with responses from “not at all” to “very much” to assess all functioning and symptoms items and two 7-point Likert scales for overall health and overall QoL. Responses to all items are then converted to a 0 to 100 scale using a standard scoring algorithm. Higher scores on the functional scales represent higher levels of functioning. Higher scores on the global health status/QoL scale represent higher health status/quality of life. Higher scores on symptom scales/items represent more extreme symptoms.

- European Organization for Research and Treatment of Cancer Multiple Myeloma module (EORTC QLQ-MY20): The QLQ-MY20 is a myeloma-specific module developed by the EORTC group specifically to assess quality of life in patients with multiple myeloma. It contains 20 items which use 4-point Likert scales, and are grouped into 2 functional scales (future perspective, body image) and 2 symptom scales (disease symptoms, side effects of treatment). Higher scores on the functional scales represent better functioning. Higher scores on the symptom scales/items represent more extreme symptoms.
- European Organization for Research and Treatment of Cancer - chemotherapy-induced peripheral neuropathy (EORTC QLQ-CIPN20): The EORTC QLQ-CIPN20 is a module developed by the EORTC group to assess chemotherapy-induced peripheral neuropathy. It contains 20 items which can be grouped into a sensory subscale (9 items), motor subscale (8 items) and autonomic subscale (3 items).

### 3.4. Baseline Variables

See [Section 3.4 of the master SAP](#) for the definition of baseline variables.

### 3.5. Safety Endpoints

See [Section 3.5 of the master SAP](#) for the definition of the safety endpoints.

## 4. ANALYSIS SETS (POPULATIONS FOR ANALYSIS)

See [Section 4 of the master SAP](#) for definitions of analysis sets.

## 5. GENERAL METHODOLOGY AND CONVENTIONS

### 5.1. Hypotheses and Decision Rules

#### 5.1.1. Hypotheses and Sample Size

##### 5.1.1.1. Phase 1b

[figure not shown]
**The primary objective in the Phase 1b part of the study is to assess safety and tolerability of elranatamab in combination with nirogacestat in order to select a RP2D for the combination therapy. There is no statistical hypothesis for the Phase 1b part of the study. A BLRM will be utilized for dose escalation of elranatamab. The dosages of elranatamab and nirogacestat for each dose level are listed in**

Table 2. Study Intervention Dose [Levels and Administration](#)

**Table 2. Study Intervention Dose Levels and Administration**

Dose Levels (DL)	Elranatamab	Nirogacestat
1 (starting dose level)	Priming Dose: 4 mg C0D1 SC Full Dose: 4 mg C1D1 SC, weekly thereafter b	100 mg PO BID continuous starting on C1D1 until response a
2	2 Step-up Priming Dose: 4 mg C0D1 SC / 8 mg C0D4 SC Full Dose: 12 mg C1D1 SC, weekly thereafter b	100 mg PO BID continuous starting on C1D1 until response a
3	2 Step-up Priming Dose: 12 mg C0D1 SC / 32 mg C0D4 SC Full Dose: 32 mg C1D1 SC, weekly thereafter b	100 mg PO BID continuous starting on C1D1 until response a
Nirogacestat De-Escalation Levels		
3A	2 Step-up Priming Dose: 12 mg C0D1 SC / 32 mg C0D4 SC Full Dose: 32 mg C1D1 SC, weekly thereafter b	100 mg PO QD continuous starting on C1D1 until response a
4A	2 Step-up Priming Dose: 12 mg C0D1 SC / 32 mg C0D4 SC Full Dose: 76 mg C1D1 SC, weekly thereafter b,c	100 mg PO QD continuous starting on C1D1 until response a
3B	2 Step-up Priming Dose: 12 mg C0D1 SC / 32 mg C0D4 SC Full Dose: 32 mg C1D1 SC, weekly thereafter b	50 mg PO QD continuous starting on C1D1 until response a
4B	2 Step-up Priming Dose: 12 mg C0D1 SC / 32 mg C0D4 SC Full Dose: 76 mg C1D1 SC, weekly thereafter b,c	50 mg PO QD continuous starting on C1D1 until response a

- a. For Dose levels 3A/3B and 4A/4B, nirogacestat will be adjusted to 50 mg QD continuous at time of confirmed VGPR. Once CR (or better) is confirmed, nirogacestat will be permanently discontinued. For all other dose levels, nirogacestat can be continued or adjusted based on this guidance, per investigator discretion. See Section 6.1.1.5.
- b. Starting at Cycle 7, if a participant has received QW dosing for at least 6 cycles and PR or better persisting for ≥2 months, dose interval will be changed from QW to Q2W. See Schedule of Activities.
- c. For participants on Dose levels 4A and 4B receiving CCI dosing, CCI the dose interval will be changed to CCI

090177e1a0f4f44c\Approved\Approved On: 14-Jun-2024 22:12 (GMT)

CCI

### **Sample Size Estimation**

A minimum of 2-6 DLT-evaluable participants (as defined in [Section 4 in the master SAP](#)) will be treated at each dose level of elranatamab. The actual number of participants to be enrolled will depend on the number of dose levels evaluated and the number of participants treated at each dose level. Therefore, it cannot be determined in advance.

It is estimated that approximately up to 30 DLT evaluable participants will be enrolled and treated with elranatamab combination which will include at least 6 DLT evaluable participants treated at the elranatamab combination MTD level and at least 6 DLT evaluable participants at the elranatamab combination RP2D level.

If any participant is deemed non-evaluable for DLT, additional participants may be enrolled to ensure there are a sufficient number of evaluable participants in the Phase 1b of the sub-study.

#### **5.1.1.2. Phase 2**

The primary endpoint in the Phase 2 part of the study is ORR per IMWG response criteria as determined by investigator. No hypothesis significance testing will be performed. Instead a Bayesian dual-criterion design will be used to estimate the true ORR of elranatamab in combination with nirogacestat. With this design, the following criteria are defined:

- Bayesian statistical significance: Substantial evidence that the true ORR exceeds a null value. For the elranatamab combination therapies, Bayesian statistical significance will be achieved if the posterior probability of the true ORR  $\geq 65\%$  exceeds 0.95;

- Clinical relevance: The minimum ORR threshold that could justify further development of a combination. For the elranatamab combination therapies, it is defined as the median of the posterior distribution of the true ORR exceeding 75%.

The analysis will use a Beta-binomial model (binomial sampling for number of responders and a Beta prior distribution). A minimally informative beta prior distribution of the true ORR will be used. It is assumed a priori that the true mean ORR for a combination is 65%, so the prior distribution will be Beta (1.3, 0.7). Using this prior and based on the dual criteria defined above, approximately 50 participants will be enrolled in the Phase 2 part of the sub-study and a minimum of 38 objective responses are required to achieve the dual criteria in 50 participants. With exactly 38 objective responses in 50 participants, the observed ORR is 76% with median 75.9% and 90% credible interval of (65.3%, 84.7%) based on the posterior distribution.

### 5.1.2. Decision Rules

#### 5.1.2.1. Phase 1b

##### Identification of MTD

[figure not shown]
The dosing decision and estimation of the MTD/MAD for each combination will be guided by the estimation of the probability of DLT during the DLT observation period. Other evidence such as safety data beyond DLT window, clinical activity, PK, and PD data will also be evaluated in determining RP2D.

##### Assessment of Participant Risk

After each dosing cohort of participants completes the DLT observation period, the posterior distribution for the risk of DLT for each dose combination will be evaluated. The posterior distributions will be summarized to provide the posterior probability that the risk of DLT lies within the following intervals.

- Underdosing: [0, 0.16);
- Target toxicity: [0.16, 0.33);
- Excessive toxicity: [0.33, 1].

CCI

### 5.1.2.2. Phase 2

The Phase 2 part of this sub-study is designed to have an interim analysis for futility and a primary analysis. The interim analysis will be conducted after the first 25 participants are treated and followed for at least 2 post-baseline disease assessments in this sub-study. The primary analysis will be conducted once all participants have been followed for response for at least 6 months or have otherwise discontinued response assessments within the first 6 months of treatment.

Table 3 presents the operating characteristics of this 2-stage design, ie, the probability of early trial termination at the interim futility analysis and the probability of observing the critical number of objective responses (i.e.,  $\geq 38$  objective responses in 50 participants) at the primary analysis if the true ORR ranges from 65% to 90%. Specifically,

- If the true ORR = 65%, the probability of stopping the study due to futility at the interim analysis is 0.533, and the probability of observing critical number of responses at the primary analysis is 0.064.
- If the true ORR = 80%, the probability of stopping the study due to futility at the interim analysis is 0.047, and the probability of observing critical number of responses at the primary analysis is 0.806.

**Table 3. Operating Characteristics of Bayesian 2-Stage Dual-Criterion Design**

True ORR	Prob of Exceeding Futility Boundary at the Interim (R1/N1 <17/25)	Prob of GO Decision at the Primary Analysis* (R/N $\geq 38/50$ )	Prob of No-GO Decision at the Primary Analysis* (R/N <38/50)
65%	0.533	0.064	0.403
70%	0.323	0.218	0.459
75%	0.149	0.502	0.349
80%	0.047	0.806	0.147
85%	0.008	0.967	0.025
90%	<0.001	0.999	0.001

\* The study does not meet futility criteria at the interim analysis and continues to the primary analysis.

ORR = objective response rate;

R1 = Minimum number of responses required at the interim futility analysis to continue the study;

N1 = Number of participants at the interim analysis;

R = Minimum number of responses required to meet the dual criteria at the primary analysis;

N = Number of participants at the primary analysis.

At the time of the primary analysis, the critical number of objective responses to be observed will be updated based on the actual number of participants enrolled and treated.

Meeting the dual criteria described above will be considered preliminary evidence that the combination therapy may provide clinically meaningful treatment effect in ORR. However,

090177e1a0f4f44c\Approved\Approved On: 14-Jun-2024 22:12 (GMT)

the decision as to whether a combination will be developed further will depend upon the observed results of both the primary and key secondary efficacy endpoints. As a result, exceeding the critical number of objective responses described above may be sufficient, but may not be necessary, for justifying further development of a combination therapy.

## 5.2. General Methods

Unless otherwise specified, all analyses will be performed for Phase 1b and Phase 2 separately and with the cohort of RP2D in Phase 1b and Phase 2 combined.

For the Phase 1b part of the study, all analyses will be performed by dose level and with all dose levels combined.

See [Section 5.2 of the master SAP](#) for the detail of the general statistical methods.

## 6. ANALYSES AND SUMMARIES

### 6.1. Primary Endpoints

#### 6.1.1. Phase 1b

DLT rate is calculated as the number of DLT-evaluable participants with DLTs in the DLT observation period divided by the number of DLT-evaluable participants in the DLT observation period.

Analyses of DLT will be performed on DLT Evaluable Analysis Set as defined in [Section 4 of the master SAP](#). DLT rate will be summarized and listed by dose levels. Participants without DLTs who do not receive at least 80% of the planned dose of elranatamab or 75% of the planned dose of nirogacestat are not evaluable for DLT. For calculation of relative dose in the DLT observation period, the denominator (planned dose) for nirogacestat is based on the nominal cycle length of 28 days. For example, for participants assigned 100 mg BID nirogacestat, the planned dosage for the DLT observational period is  $100 \times 2 \times 28 = 5600$  mg.

#### 6.1.2. Phase 2

The primary endpoint is ORR, defined as the proportion of participants with an objective response ([Section 0](#)) per IMWG response criteria as determined by investigator. Participants without documented response will be considered as non-responders.

**Primary Estimand:** the treatment effect of elranatamab in combination with nirogacestat on ORR per the IMWG criteria as determined by investigator. The estimand has the following attributes:

- Population: RRMM participants, as defined by the inclusion and exclusion criteria to reflect the targeted population of the treatment, who received at least 1 dose of study intervention.
- Variable: Objective response ([Section 0](#)) per IMWG response criteria as determined by investigator.

- Intercurrent events: All data collected after an intercurrent event of subsequent anti-cancer therapy will be excluded. All response assessments regardless of gaps in disease assessments will be considered. Participants who do not have a post-baseline disease assessment due to early PD, who receive anticancer therapies other than the study intervention prior to achieving an objective response, or who die, experience PD, or stop disease assessments for any reason prior to achieving an objective response will be counted as non-responders.
- Population-level summary measure: ORR defined as the proportion of participants in the analysis population with an objective response. The median and its corresponding 2-sided 90% credible interval of ORR in the analysis population based on the posterior distribution will be calculated.

Additionally, the observed point estimate of ORR will be calculated along with the 2-sided 90% CIs using the Clopper-Pearson method (exact CI for a binomial proportion).

The frequency (number and percentage) of participants with BOR by investigator in each response category will be summarized: sCR; CR; VGPR; PR; MR; SD; PD; Not evaluable (NE)/unknown.

In addition, the following response categories will be calculated along with corresponding 2-sided exact 95% CIs using the Clopper-Pearson method:

- VGPR or better (sCR + CR + VGPR);
- Clinical benefit (sCR + CR + VGPR + PR + MR).

BOR will be assessed programmatically based on reported timepoint responses by investigator recorded at evaluation time points from the date of first dose until confirmed disease progression, death or start of new anticancer therapy using IMWG response criteria. BOR needs to be confirmed according to IMWG response criteria (Table 4). If a participant meets multiple criteria in determining confirmed BOR, the order of criteria in this table will be used to define the hierarchy. Twenty-eight days is the scheduled gap between the disease assessments after cycle 1. If a confirmation is to be done on the same day, a different sample is required for confirmation. A confirmatory response assessment may be performed >28 days following the initial response assessment, allowing for a maximum of 1 intervening missing or not evaluable assessment.

For participants with EMD at baseline, MR or better (for those with target plasmacytomas) and CR or better (for those with non-target non-bone EMD only) cannot be confirmed until a post-baseline EMD assessment is performed.

The rules for PD confirmation apply to both confirmed PD as BOR and confirmed PD after BOR (for time-to-event endpoint analyses), and the PD date is the date of the initial PD assessment.

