## 4. ANALYSIS SETS (POPULATIONS FOR ANALYSIS)

For purposes of analysis, the following analysis sets are defined:

Participant Analysis Set	Description
DLT-Evaluable Analysis Set	
The DLT-evaluable analysis set will include all enrolled participants who receive at least 1 dose of the study intervention in the Phase 1b part of the study and either experience DLT(s) or complete the DLT observation period without DLT. Participants without DLTs who receive less than the minimum requirement of the planned doses of each IP for reason other than treatment-related toxicity are not evaluable for DLTs.
 
The DLT observation period is 35 days from Cycle 0 Day 1 through Cycle 1 Day 28.

090177e196913362\Approved\Approved On: 19-Mar-2021 12:41 (GMT)

	
The minimum required exposure for DLT evaluability is defined as follows:
 
 
• For PF-06863135 (all sub-studies): 4 out of 5 planned doses during the DLT observation period. Participants must be able to receive the full dose on Cycle 1 Day 1 (-1/+3 dosing window) and not require any dose reductions during the DLT observation period;
 
• For nirogacestat (sub-study A): at least 75% of the planned doses and not require any dose reductions during the DLT observation period.
 

Safety Analysis Set	The safety analysis set will include all enrolled participants who received at least 1 dose of study intervention.
PK Analysis Set	
The PK analysis set will include all participants in the safety analysis set who have at least 1 post-dose concentration measurement.
 
The PK parameter analysis set will include all participants in the safety analysis set who have at least one of the PK parameters of interest for PF-06863135.

Immunogenicity Analysis Set	The immunogenicity analysis set will include all participants in the safety analysis set who have at least 1 sample tested for ADA.
Biomarker Analysis Set	
The biomarker analysis set will include all participants in the safety analysis set who have at least 1 baseline biomarker assessment.
 
Analysis sets will be defined separately for biomarkers based on blood, and bone marrow samples.

PRO Analysis Set	The PRO analysis set will include all participants in the safety analysis set who completed a baseline (last PRO assessment prior to or on the first dose of study intervention) and at least 1 post-baseline PRO assessment.

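### Sub-study A SAP Section 6.1.1 gives two incompatible DLT-evaluability rules: one keeps participants under-exposed because of treatment-related toxicity, the other excludes them

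*SAP*

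**What the plan says.** The master SAP fixes evaluability in two places: the Phase 1b primary estimand (Section 2.1.1, headed as applying to all sub-studies) and the DLT-Evaluable Analysis Set (Section 4). In Section 4 the group excluded for low exposure is "Participants without DLTs who receive less than the minimum requirement of the planned doses of each IP for reason other than treatment-related toxicity". The minimum is "4 out of 5 planned doses during the DLT observation period" for elranatamab and "at least 75% of the planned doses and not require any dose reductions during the DLT observation period" for nirogacestat. The cause of the shortfall is therefore part of the rule.

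The Sub-study A SAP adopts that set. Its Section 4 points to the master SAP, and Section 6.1.1 says "Analyses of DLT will be performed on DLT Evaluable Analysis Set as defined in" master Section 4. Section 6.1.1 then restates the exposure rule and classes this group as non-evaluable: "Participants without DLTs who do not receive at least 80% of the planned dose of elranatamab or 75% of the planned dose of nirogacestat". No cause is mentioned, and the toxicity exception appears nowhere in the Sub-study A SAP's own text.

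Section 5.1.1.1 of the Sub-study A SAP adds: "If any participant is deemed non-evaluable for DLT, additional participants may be enrolled".

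**The concern.** The DLT rate among evaluable participants is the Phase 1b primary estimand. The estimated DLT probability guides dosing and the MTD, and evaluable counts decide when there are at least 6 participants at the MTD and at the RP2D. One paragraph supplies two definitions of that set.

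They differ for one group: participants who complete the observation period without a DLT but miss enough drug, because of treatment-related toxicity, to fall below the minimum. The imported definition counts them as non-events. The restated sentence drops them and allows replacement. A programmer could reasonably follow either the cited definition or the more specific sentence after it.

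The difference does not look intended. Under DLT, the version 2 summary of changes (Table 1) lists only a clarification of the observation period. Section 2.1, on modifications, covers only movement between dose levels. Section 2 describes the document as specific to Sub-study A but gives no order of precedence against the master SAP. Sub-study B's Section 6.1.1 cites master Section 4 without restating the exposure rule, so the conflict does not arise there.

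**Working it through.** **1. The plan's own figure.** Section 6.1.1 gives the planned nirogacestat dose at 100 mg BID as 100 × 2 × 28 = 5600 mg. This reproduces. The 75% minimum is 0.75 × 5600 = 4200 mg, so more than 7 missed days of 28 falls below it.

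**2. A participant on whom the rules disagree (hypothetical).** Nirogacestat is held for 10 of 28 days for treatment-related toxicity, with no DLT and the observation period completed. Dose received is 18 × 200 = 3600 mg, and 3600/5600 = 64%.

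- Master SAP Sections 2.1.1 and 4: below the minimum, but because of toxicity, so evaluable without a DLT.
- Restated sentence in 6.1.1: "75% of the planned dose of nirogacestat are not evaluable for DLT", so excluded, and another participant may be enrolled.

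**3. What each rule estimates.** Among participants not excluded for any other reason, let d be the share with a DLT and u the share without a DLT but under-exposed because of toxicity. Participants with a DLT stay in under both rules.

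- Imported rule: d/1 = d.
- Restated rule: d/(1 − u).

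Replacements pass through the same filter, so replacing participants does not change the second target.

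The documents give neither d nor u. With d = 0.27 assumed:

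| u (assumed) | d/(1 − u) | Result |
|---|---|---|
| 0.05 | 0.27/0.95 | 0.284 |
| 0.10 | 0.27/0.90 | 0.300 |
| 0.15 | 0.27/0.85 | 0.318 |
| 0.20 | 0.27/0.80 | 0.338 |

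To reach 0.33 from d = 0.27, u must be 1 − 0.27/0.33 = 0.18.

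**4. Small cohorts, before replacement (assumed counts, 6 treated).**

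| DLTs | Toxicity-related shortfalls | Imported rule | Restated rule |
|---|---|---|---|
| 1 | 1 | 1/6 = 16.7% | 1/5 = 20.0% |
| 1 | 2 | 1/6 = 16.7% | 1/4 = 25.0% |
| 2 | 1 | 2/6 = 33.3% | 2/5 = 40.0% |

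Every participant removed is a non-event, so the observed rate can only stay the same or rise.

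**The case against.** The best defence is that the sentence is shorthand. It follows an explicit reference to master Section 4, and it omits other parts of that definition too: the full dose on Cycle 1 Day 1, no dose reductions, and completion of the observation period. What follows it explains the relative-dose denominator, so its purpose may be to introduce that calculation. With no declared change, the imported definition may be what is meant. This stands as far as it goes. A reader might infer that the Sub-study A SAP has replaced the master rule and that these participants are definitely removed. The documents do not support that, because Sections 4, 5.1.1.1 and 6.1.1 all still point to the master set. But the sentence is categorical, and nothing tells the programmer to treat it as a summary.

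A reader might also infer that excluding non-tolerators hides toxicity. It does not: no DLT leaves the numerator, and the rate moves upward. In DLT terms that is the cautious direction. The costs are a different estimand, data lost to the model, and possible extra enrolment.

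Third, the table in step 3 might suggest that the choice of rule alters a dose decision. That is not shown. With d = 0.27, 0.33 is crossed only once u exceeds about 0.18, and 2/6 already lies in the upper interval [0.33, 1]. In Section 5.1.2.1 the boundary defines intervals for the posterior distribution of DLT risk and is not a cut-off for a crude rate. The prior parameters are redacted, so the model cannot be rerun.

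Finally, the Sub-study A protocol, where the DLT definition would be, is not among the documents. If it counts toxicity-related missed dosing as a DLT, u shrinks. The master SAP rests on protocol Amendment 1 and the Sub-study A SAP on Amendment 8, so the current protocol must be checked before either wording is adopted.

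**Conclusion.** The point holds as an unresolved contradiction within Section 6.1.1, and between its restated sentence and the master SAP's estimand and analysis set. The effect is conditional. If the restated sentence is applied, participants without a DLT who were under-exposed through treatment-related toxicity leave the denominator and the model input, and the DLT rate is biased upward by a factor of 1/(1 − u) relative to the master estimand. For u between 0.05 and 0.20 that factor is about 1.05 to 1.25. The values of d, u and the cohort counts are assumptions, and the true size depends on the unseen DLT definition. In cohorts this small, one participant visibly moves the observed rate, so the primary analysis set should not rest on which sentence is read first.

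**What to change.** Reconcile Section 6.1.1 with the master estimand, master Section 4 and the current Sub-study A protocol. Two edits would do it:

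- restore the master SAP's qualifier, so that the restated sentence ends "for reason other than treatment-related toxicity are not evaluable for DLTs"; or
- delete the restated sentence, rely on master Section 4, and keep only the text on the relative-dose denominator.

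If the current protocol did intend to drop the exception, list this as a change in Table 1 and amend the estimand to match.

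A listing of participants kept evaluable under the exception, with the dose fraction received, would help dose review but is optional. The cost is one clause or one deletion, with no new data.
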